7.1 Treatments to be administered

Finerenone immediate-release (IR) tablets are light orange film-coated tablets, oval (modified oblong), containing 10 mg or 20 mg finerenone (Table 7–1). Matching placebo tablets will be supplied.

Following a Screening Visit, eligible subjects will be randomized 1:1 to either finerenone or placebo, and study drug will be dispensed according to the visit schedule (see Section 9.1).

The subject will receive the following:

- Finerenone
 - 10 mg finerenone tablet once daily (OD)
(starting dose for subjects with an eGFR between 25 to < 60 mL/min/1.73m² at the Screening Visit)
 - 20 mg finerenone tablet OD
(starting dose for subjects with an eGFR ≥ 60 mL/min/1.73m² at the Screening Visit)
- or**
- Placebo tablet OD.

Following randomization of the subject, the IxRS will determine the bottle number for the study site investigator or designee to select for the subject. The investigator at the study site is to instruct subjects to take 1 tablet OD, preferably in the morning. The first dose of study drug should be taken at the site on the same day as Visit 1 (Day 1), preferably in the morning.

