9.2.3 Visit 1 (randomization; Day 1 and baseline) - *amended*

This section was changed in Amendment 3, see Section 15.1.2.17.

All measurements on Visit 1 are to be performed on the day of the visit before first study drug intake. The following procedures and assessments will be performed at Visit 1:

- Instruct the subject on how to complete KDQOL-36 and EQ-5D-5L questionnaires; the subject completes the questionnaires (see Section 9.7.7).

- Obtain informed consent for sub-studies (see Section 9.7.8.1)
- Check inclusion and exclusion criteria (see Sections 6.1 and 6.2)
- Record use of concomitant medication (see Section 8.1)
- Record body weight (see Section 9.7.4)
- Record vital signs (see Section 9.7.5)
- Perform 12-lead ECG (see Section 9.7.6)
- Take samples (hematology, HbA_{1c}, chemistry, urinalysis) for central laboratory evaluations (see Section 9.7.2.1)
- Take samples (potassium, creatinine) for local safety laboratory evaluations (see Section 9.7.2.2)
- Optional: if the subject had signed informed consent for the sub-study, obtain respective samples for biomarkers (see Section 9.7.8.1.2) and/or iohexol clearance (see Section 9.7.8.1.3), perform echocardiography (see Section 9.7.8.1.1)
Note: Time window for the echocardiography at Visit 1 is -14/+7 days. On the day the echocardiography is performed, a blood sample should also be drawn to assess the echo biomarkers.
- Randomization to finerenone or placebo once daily (see Section 7.1)
- Dispense the study drug (see Section 7.2)
- Record adverse events (see Section 9.6.1), accounting for the rules of assessment and documentation (see Section 9.6.1.3)
- First administration of study drug.

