4.3 Handling of Missing Data

All missing or partial data will be presented in the subject data listing as they are recorded on the Case Report Form (CRF).

General rules

When appropriate, the following rules will be implemented so as not to exclude subjects or observations from statistical analyses due to missing or incomplete data.

Concomitant medications with missing start and stop date but flagged as being ongoing at end of study will be considered to have started prior to study medication start and end after stop of study medication. The start and end reference period will be imputed as “before” for the medication start and as “during/after” for the medication end.

In case of (partially) missing dates for interruptions or permanent stop of study medication intake, a ‘worst-case’ approach will be applied to impute the start and end dates of study medication intake as the minimum and maximal possible dates, i.e.:

- first month of the year, or first day of the month for a partially missing start date, and
- last month of the year, or last day of the month for a partially missing end date.

If a subject died earlier than the imputed worst study medication end date, the death date will be taken as the study medication end date. However, if these imputations lead to a temporal overlap between different exposure date records, the imputed dates will be adjusted so that no overlap exists and the time on the higher dose is maximized. The date of first exposure to treatment is not expected to be missing as the patients are instructed by the investigator to take their first dose of study drug directly at Visit 1, but in the very rare case that this date is not recorded, it will be imputed according to the rules outlined above for missing start dates, but not earlier than the randomization date.

When only partial dates are available for clinical events in the efficacy analysis, a median imputation rule will be used:

- For example if the day is missing and the month is July, then day 16 is chosen.
- If the number of potential values is even, the lower of the 2 middle numbers is taken. For example, if the day is missing and the month is June, then day 15 is imputed. The same rule applies if the day and month are missing, e.g. if the year is 2017 and the day and month are missing, 2nd July is taken.

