4.5.1 Baseline values

Baseline values will be defined as the last non-missing measurement before or on the day of randomization. If the last observation available prior to randomization is the measurement from the Screening Visit, this would be used as the baseline value. This also includes assessments from a local laboratory, in case that prior to randomization, no assessment from the central laboratory is available. Otherwise baseline will be missing. The measurement from the Run-in Visit will not be used as a baseline value unless otherwise specified.

If more than one measurement was planned for a scheduled visit, for example blood pressure measurements and heart rate, the mean value of these measurements per time point prior to randomization will be used as the baseline value.

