4.5.3 Other data handling

Only the data provided by the central laboratory will be used for analysis, values from local laboratories will not be used in the statistical analysis and will be listed only unless there are no values from the central laboratory available for baseline.

In case of retests for Run-in and Screening visits, the closest measurement prior to randomization will be used for analysis instead of the scheduled measurements. At all visits starting at Visit 1 and if not stated otherwise, only the values at scheduled measurements will

be used for analysis. In the unexpected case that more values than planned are available for a scheduled visit, only the first valid value will be used.

For the derived visit “Any time post-baseline” (applicable for efficacy) this will include any measurement after date of randomization, including unscheduled assessments. For the derived visit “Any treatment-emergent” (applicable for safety), only assessments on or after study medication start date until 3 days after the date of any temporary or permanent interruption of study drug, including unscheduled assessments, will be considered.

For those laboratory values which are <LLOQ (Lower limit of quantification), half the value of the LLOQ will be used for analysis. Differences between 2 values <LLOQ will be assigned values of 0. Ratios between 2 values <LLOQ will be assigned a value of 1. For values which are >ULOQ (Upper limit of quantification), the ULOQ will be used for analysis. This rule does not apply to the finerenone plasma concentration data.

In case of log-normally distributed data, descriptive statistics other than minimum, maximum and median will only be calculated if at least 2/3 of the individual data were measured and were above the lower limit of quantification. In tables showing descriptive statistics, where values below LLOQ are included, these descriptive statistics will be marked.

Urinalysis is assessed 3 times per visit. UACR will be determined 3 times at each visit from first morning void urine samples collected on 3 consecutive days. For the analyses of UACR, the 3 measurements at one visit will be combined provided that at least 2 measurements are available. First, the coefficient of variation (CV) will be calculated for the 3 values as follows considering the log-normal distribution for UACR [7]:

$$CV = \sqrt{\exp(SD_{\ln}^2) - 1},$$

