6.4.1 Adverse events

Adverse events (AEs) will be coded using the Medical Dictionary for Regulatory Activities (MedDRA, latest version available prior to data base freeze). A listing will be provided linking the original investigator terms and the coded terms. AEs will also be presented grouped by SMQs.

AEs that started or worsened after the first dose of study drug up to 3 days after any temporary or permanent interruption of study drug will be considered as treatment emergent AEs (TEAEs).

An overall summary of all AEs and TEAEs will be generated by treatment group.

The number of subjects with TEAEs, pre-randomization AEs, post-treatment AEs occurring more than 3 days after any temporary or permanent stop of study drug, treatment-emergent SAEs, treatment-emergent study drug-related AEs, treatment-emergent study drug-related SAEs, treatment-emergent SAEs and TEAEs causing permanent discontinuation of study drug, treatment-emergent non-serious AEs, non-serious AEs, TEAEs by maximum intensity, treatment-emergent SAEs by maximum intensity, drug-related TEAEs by maximum intensity, TEAEs by worst outcome and treatment-emergent SAEs by worst outcome will be summarized by treatment group using MedDRA terms grouped by Primary System Organ Class and Preferred Term.

To comply with local regulatory requirements in Japan, some cardiovascular disease-related outcome events will also be documented as (S)AEs in Japan. These will be included in the outcome event tables (see section 6.2.3.6), and to avoid double-counting of such events, they will not be included in the adverse event summary tables or listings. A separate listing will be generated for all AEs excluded from the AE analysis due to double reporting in Japan.

In case of events with different intensity within a subject, the maximum reported intensity will be used. If intensity is missing, the event will be considered as severe. If the same event is considered as both unrelated and related to the study drug within a subject, the event will be reported as related to study drug. If the drug relationship is missing, the event will be considered as being related to the study drug.

These further safety variables are listed in section 10.3.4 of the protocol:

- Number of subjects with hospitalization for hyperkalemia
- Number of subjects discontinuing study drug permanently due to hyperkalemia
- Number of subjects with hospitalization for worsening of renal function

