6.4.2 Laboratory parameters

The number of subjects with treatment-emergent (until 3 days after any temporary or permanent interruption of study drug) abnormal laboratory values above or below the normal range will be tabulated by the laboratory parameter and treatment group.

Summary statistics including changes to baseline will be calculated by treatment group and visit for all quantitative laboratory parameters, e.g. for hematology, HbA1c, clinical chemistry and urinalysis. Geometric statistics and ratios to baseline will be presented for creatinine and UACR instead of arithmetic statistics with changes from baseline. For eGFR the relative change will be displayed in addition to the absolute change from baseline.

Summary statistics for serum potassium, eGFR and serum creatinine will also be repeated by treatment group and visit separately for the following subgroups:

- eGFR category at baseline (eGFR <30, 30 to <60, 60 to <90 and ≥ 90 mL/min/1.73m²)
- Baseline serum potassium value (≤ 4.8 mmol/L, >4.8 to 5.0 mmol/L, >5.0 mmol/L)

The following special safety parameters will be further assessed by displaying the number of subjects with treatment-emergent safety events. This will also be performed by visit and by stratification factors. The summaries will be performed for the number of subjects with:

- Absolute value of serum potassium >5.5 mmol/L and >6.0 mmol/L,
- Relative decrease from baseline in eGFR of $\geq 30\%$, $\geq 40\%$, $\geq 50\%$ and $\geq 57\%$
- Absolute value of eGFR <30 mL/min/1.73m².

The percentage of subjects with the respective treatment-emergent events (non-stratified) will be compared between the finerenone and the placebo or active control group by applying separate explorative χ^2 tests with continuity correction. If the expected number of subjects in at least 1 cell of the 2x2 contingency table is less than 5 (see reference 5), Fisher's exact test will be applied instead of the χ^2 test. Estimates and two-sided 95% confidence intervals will be provided for each treatment group and the treatment differences. Clopper Pearson confidence intervals will be calculated for each treatment group, while for treatment differences, due to the computational burden of exact unconditional confidence limits, the Wald asymptotic confidence limits will be calculated.

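### SAP 4.5.3 opens the treatment-emergent laboratory window on the study-drug start date itself, so the pre-dose Visit 1 baseline sample also counts as treatment-emergent

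*SAP*

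**What the plan says.** Four rules meet on Day 1.

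- **Sampling.** Protocol 9.2.3: "All measurements on Visit 1 are to be performed on the day of the visit before first study drug intake". The schedule of evaluations places a full central laboratory sample at this visit.
- **First dose.** Protocol 7.1 asks for it at the site on the Visit 1 day. SAP 4.3 relies on the same plan: "the patients are instructed by the investigator to take their first dose of study drug directly at Visit 1".
- **Baseline.** SAP 4.5.1: "Baseline values will be defined as the last non-missing measurement before or on the day of randomization".
- **Treatment-emergent laboratory window.** SAP 4.5.3: "only assessments on or after study medication start date until 3 days after the date of any temporary or permanent interruption of study drug", unscheduled assessments included.

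SAP 6.4.2 applies the treatment-emergent condition to out-of-range values and to special safety parameters such as "Absolute value of serum potassium >5.5 mmol/L and >6.0 mmol/L" and eGFR below 30. For the out-of-range counts it restates the end of the window but not its start, so 4.5.3 governs the start. The special safety parameters are compared by exploratory chi-square or Fisher tests, with percentages per arm and confidence limits for treatment differences. Aalen-Johansen curves are planned for potassium.

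**The concern.** A sample drawn before the first tablet cannot be treatment-emergent, yet the date rule admits it. Nothing in SAP 4.5.3, 6.4.1 or 6.4.2 removes the baseline record, uses clock time, or requires a baseline inside the threshold.

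The neighbouring definitions avoid the overlap. The efficacy counterpart in the same paragraph reads "this will include any measurement after date of randomization". The adverse-event rule in SAP 6.4.1 begins "AEs that started or worsened after the first dose of study drug up to 3 days after any". Protocol 10.3.4.2 compares these same laboratory events over post-baseline time.

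Affected subjects are foreseeable:

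- The potassium limit of 4.8 mmol/L applies at Run-in and Screening, not at Visit 1.
- Protocol 9.7.1 reports falsely high central-laboratory potassium from handling and transport, and the analysis uses central values.
- Entry allows eGFR from 25, and SAP 4.5.4 has baseline categories for eGFR <30 and potassium >5.0.

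Hyperkalaemia is one of the main risks the protocol identifies, so its laboratory count should contain only values observed on drug.

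**Working it through.** The plan states no figure for this, so there is none to reproduce. The check has two parts.

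**1. Date logic.** Take a constructed subject with randomization, Visit 1 sample and first dose all on one date.

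| Record | Potassium (mmol/L) | Baseline rule: date ≤ randomization date | SAP 4.5.3: date ≥ start date | Date > start date |
|---|---|---|---|---|
| Screening | 4.7 | superseded by Visit 1 | no | no |
| Visit 1, pre-dose | 5.6 | **baseline** | **treatment-emergent** | no |
| Visit 2 | 5.0 | no | treatment-emergent | treatment-emergent |

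As written, the subject is a case of potassium >5.5 although no on-drug value exceeded 5.5. With a window that starts after the start date, there is no event.

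Relative eGFR falls are safe, because the baseline compared with itself gives 100 × (b − b)/b = 0%.

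**2. Size.** Let q be the share beyond the threshold on the pre-dose sample, p the on-drug proportion among the others, and r the proportion of the pre-dose exceeders who exceed again on drug.

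- As written: (1 − q)p + q
- Corrected window: (1 − q)p + qr
- Wrongly added: q(1 − r)

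The change in the risk difference between arms is q(r₁ − r₀), where 1 is finerenone and 0 is placebo. It cannot exceed q.

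For potassium, take r = p, meaning that pre-dose exceeders behave like everyone else in their arm. The corrected proportion is then p, and the difference as written is (1 − q)(p₁ − p₀). All rates below are assumptions.

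| True placebo / finerenone | q | As written | Difference, true → as written (points) | Ratio, true → as written |
|---|---|---|---|---|
| 5% / 10% | 0.5% | 5.48% / 10.45% | 5.0 → 4.98 | 2.00 → 1.91 |
| 5% / 10% | 2% | 6.90% / 11.80% | 5.0 → 4.90 | 2.00 → 1.71 |
| 2% / 4% | 0.5% | 2.49% / 4.48% | 2.0 → 1.99 | 2.00 → 1.80 |
| 2% / 4% | 2% | 3.96% / 5.92% | 2.0 → 1.96 | 2.00 → 1.49 |

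Example for the second row: 0.98 × 5% + 2% = 6.90%; 0.98 × 10% + 2% = 11.80%; difference 4.90 points; ratio 11.80/6.90 = 1.71.

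With about 7400 randomized (SAP 3), q of 0.5-2% means 7400 × 0.005 = 37 to 7400 × 0.02 = 148 subjects with a pre-dose value inside the window. If exceeders tend to exceed again (r above p), fewer are wrongly added than the table implies.

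For eGFR <30 and many out-of-range values, r is probably high, because a subject at 27 before drug is likely to be below 30 again. Then q(1 − r) is small: only subjects never again beyond the threshold on drug are added.

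**The case against.** Several points on the other side stand.

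- **No risk ratio is planned.** SAP 6.4.2 reports percentages and differences, and the difference hardly changes. The fall in the ratio matters only to a reader who divides the two reported percentages.
- **eGFR <30.** A reader might infer that the window turns this count into a count of baseline status. It does not. The protocol itself plans an absolute threshold without a baseline condition, and most subjects low at baseline would probably be counted at later visits under any window.
- **A step at time zero in the potassium curves.** This is tempting to infer, but SAP 6.4.2 starts the time at risk at first intake, which can be read as leaving out a pre-dose sample. The text does not settle it.
- **Restricting counts to subjects not already beyond the threshold.** That may be informative, but it would change the absolute-value count planned in protocol 10.3.4.2. It is an analysis preference, not a correction of this window.
- **Visibility.** The special safety counts are also shown by visit. SAP 4.5.4 breaks treatment-emergent hyperkalaemia down by baseline potassium, so if that variable is the laboratory one, spurious events can fall only in the category above 5.0.
- **Frequency.** Entry required potassium of at most 4.8 at Screening, no more than two weeks earlier. No document gives the share above 5.5 at Visit 1.

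It can also be said that programmers exclude baseline-flagged records by habit, and that the rest of the documents points to a post-dose meaning. Both are plausible, but the SAP's text says otherwise, and an unstated convention is not a pre-specified rule.

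**Conclusion.** The overlap is real on the SAP's wording in the planned case, where the first dose falls on the Visit 1 date. It does not arise if dosing began on a later day or if the baseline came from Screening.

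Its effect is limited. Incidence of absolute-threshold laboratory events is inflated about equally in both arms (for potassium >5.5, by up to about 0.5-2 points if 0.5-2% exceed it pre-dose), and relative comparisons drift towards 1. The planned risk difference moves only from 5.0 to 4.98-4.90 points at assumed risks of 5% and 10%. That small change assumes that pre-dose exceeders exceed again at their arm's general rate. Other patterns change the difference by q(r₁ − r₀).

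Hyperkalaemia reported as an adverse event, relative eGFR decreases and all efficacy analyses are untouched, and the affected tests are exploratory. This is a minor to moderate correction, not one on which the trial's conclusions depend.

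**What to change.** In SAP 4.5.3, define the window as assessments dated after the study medication start date. Alternatively, keep the start date inclusive but exclude the record used as baseline and any other pre-dose Visit 1 sample. Either version agrees with the post-baseline comparison in protocol 10.3.4.2 and with the adverse-event definition. State in SAP 6.4.2 that the same rule governs the out-of-range counts, the potassium and eGFR threshold counts, and the potassium Aalen-Johansen curves.

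The cost is one phrase, one cross-reference and a derivation flag, with no new data. A rule based on clock time is less safe: the protocol calls for exact intake and sampling times at the pharmacokinetic visits, but does not show that they are recorded for the Visit 1 bloods.

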4.5.4 Subgroup analyses

Exploratory subgroup analysis will be performed for the primary and secondary efficacy variables. The subgroup analyses will include the randomization stratification factors. The list of key subgroups (in addition to the stratification factors) and other subgroups analyzed is specified below. Analysis will include descriptive statistics, graphical display of estimated treatment effects with 95%-CIs in a forest plot and a statistical test for interaction.

Stratification factors:

- Region (North America, Latin America, Europe, Asia, Others)
- eGFR category at screening (eGFR 25 to <45, 45 to <60 and ≥ 60 mL/min/1.73m²)
- Type of albuminuria at screening (high albuminuria, very high albuminuria)
- History of CVD (present, absent)

Persistent high albuminuria is defined as UACR of ≥ 30 mg/g (≥ 3.4 mg/mmol) but <300 mg/g (<33.9 mg/mmol) in 2 out of 3 first morning void samples. Persistent very high albuminuria is defined as UACR of ≥ 300 mg/g (≥ 33.9 mg/mmol) in 2 out of 3 first morning void samples.

Key subgroups (in addition to stratification factors)

- Sex (male, female)
- Race (white, black, Asian, other)
- Age at run-in visit (<65, ≥ 65 years)
- eGFR category at baseline (eGFR <25, 25 to <45, 45 to <60 and ≥ 60 mL/min/1.73m²)
- Type of albuminuria at baseline (normalalbuminuria (UACR <30 mg/g), high albuminuria, very high albuminuria)
- Baseline serum potassium value (\leq median and $>$ median in the FAS)
- UACR at baseline (\leq median and $>$ median in the FAS)
- Systolic blood pressure at baseline (\leq median and $>$ median in the FAS)
- Baseline BMI (<30, ≥ 30 kg/m²)
- Hemoglobin A1C ($\leq 7.5\%$ / $> 7.5\%$)
- SGLT-2 inhibitors treatment at baseline (yes, no)
- GLP-1 agonists treatment at baseline (yes, no)

Other subgroups

- Baseline serum potassium value (≤ 4.5 , > 4.5 mmol/L)

- Baseline serum potassium (by quartiles in the FAS: $\leq Q1$, $>Q1$ and $\leq Q2$, $>Q2$ and $\leq Q3$, $>Q3$)
- Baseline serum potassium value (≤ 4.8 mmol/L, >4.8 to 5.0 mmol/L, >5.0 mmol/L)
- Baseline hemoglobin A1C (by quartiles in the FAS: $\leq Q1$, $>Q1$ and $\leq Q2$, $>Q2$ and $\leq Q3$, $>Q3$)
- Baseline C-reactive protein (by quartiles in the FAS: $\leq Q1$, $>Q1$ and $\leq Q2$, $>Q2$ and $\leq Q3$, $>Q3$)
- Systolic blood pressure at baseline (<130 mmHg, 130 to <160 mmHg, and ≥ 160 mmHg)
- Age at run-in visit (18 to 44 years, 45 to 64 years, 65 to 74 years, 75 years and over)
- Ethnicity (hispanic or latino, not hispanic or latino, not reported)
- Baseline BMI (<20 , 20 to <25 , 25 to <30 , 30 to <35 , ≥ 35 kg/m²)
- Baseline weight (<60 , 60 to <90 , ≥ 90 kg)
- eGFR category at baseline (eGFR <30 , 30 to <60 , 60 to <90 and ≥ 90 mL/min/1.73m²)
- eGFR at baseline 25 to <45 ml/min/1.73m² and baseline serum potassium value >4.5 mmol/L (yes, no)
- ACEI at baseline (yes, no)
- ARB at baseline (yes, no)
- Beta-blocker at baseline (yes, no)
- Diuretic at baseline (yes, no)
- Statins at baseline (yes, no)
- Other anti-diabetic treatment at baseline: insulin and analogues (yes, no); DPP-4 inhibitors (yes, no); biguanides (yes, no); sulfonylureas (yes, no); alpha glucosidase inhibitors (yes, no); meglitinides (yes, no); thiazolidinediones (yes, no)
- Potassium supplementation at baseline (yes, no)
- Potassium lowering agents (including binders) at baseline (yes, no)
- Potency of concomitant CYP3A4 inhibitor medication at baseline (strong, unclassified, moderate, weak, none)
- Potency of concomitant CYP3A4 inducer medication at baseline (strong, unclassified, moderate, weak, none)
- Baseline waist circumference (normal [men <94 cm, women <80 cm], increased [men 94 - 102 cm, women 80 - 88 cm], substantially increased [men >102 cm, women >88 cm])

If the result for a subgroup cannot be calculated due to a small sample size or number of events, then this subgroup will be dropped.

Individual country analyses, e.g. for Japan, required for regulatory purposes, will be included in a country-specific study SAP.

For the safety variables

- Number of subjects with hyperkalemia (treatment-emergent only)
- Number of subjects with hospitalization for hyperkalemia
- Number of subjects discontinuing study drug permanently due to hyperkalemia
- Number of subjects with hospitalization for worsening of renal function
- Number of subjects discontinuing study drug permanently due to worsening of renal function

exploratory subgroup analyses will be performed in the following selected subgroups:

- eGFR category at baseline (eGFR <25, 25 to <45, 45 to <60 and ≥ 60 mL/min/1.73m²)
- eGFR category at baseline (eGFR <30, 30 to <60, 60 to <90 and ≥ 90 mL/min/1.73m²)
- Baseline serum potassium value (≤ 4.5 , > 4.5 mmol/L)
- Baseline serum potassium value (≤ 4.8 mmol/L, > 4.8 to 5.0 mmol/L, > 5.0 mmol/L)
- Hyperkalemia (based on MLG) in medical history (yes, no)
- Selected anti-diabetic treatments at baseline: DPP-4 inhibitors (yes, no); GLP-1 agonists (yes, no); SGLT-2 inhibitors (yes, no)
- Diuretic at baseline (yes, no)
- Potency of concomitant CYP3A4 inhibitor medication at baseline (strong, unclassified, moderate, weak, none)
- Age at run-in visit (18 to 44 years, 45 to 64 years, 65 to 74 years, 75 to 84 years and 85 years and over)
- Region (North America, Latin America, Europe, Asia, Others)
- Sex (male, female)
- Hepatic impairment in medical history (yes, no)
- Hepatic impairment at baseline (based on laboratory measurements) (likely Child Pugh A, likely Child Pugh B, certain Child Pugh B)

